8.6 Dose Expansion

An expansion cohort will be enrolled after the MTD has been determined in the escalation portion of the study. A maximum of 6 patients will be enrolled in the expansion cohort, dosed at the MTD. Expansion patients will continue to be monitored for safety to ensure that the DLT risk does not exceed 30%. Specifically, if more than 2 patients in the expansion cohort experience a DLT, an ad hoc SRC meeting may be convened to discuss the acceptability of the MTD.

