Once the MTD is determined, an additional 6 patients will be treated in an expansion cohort at this dose level or at a lower dose level determined to be the RP2D. For the expansion cohort, patients will continue to be monitored for occurrence of DLTs. If 2 of the first 5 patients or if ≥ 2 of 6 patients experience a DLT, the Principal Investigator will discuss with all study Investigators and with the Medical Monitor and/or SRC whether further addition of patients is needed to re-assess the MTD. Monitoring of all safety and toxicity data will be done by the Principal Investigator and the SRC on a real-time basis.

In the absence of treatment delays due to AEs, treatment for an individual patient may continue until the completion of standard therapy (until the end of Adjuvant Cycle 6) or until one of the following criteria applies:

- Disease progression

- Intercurrent illness that prevents further administration of treatment
- Unacceptable AEs
- Patient decides to withdraw from the study
- General or specific changes in the patient's condition render the patient unacceptable for further treatment in the judgment of the Investigator
- Clinical progression
- Patient noncompliance
- Pregnancy
- Termination of the study by the Sponsor
- The drug manufacturer can no longer provide the study agent

Toxicities requiring dosing delay or modifications will result in dose adjustments as outlined in [Section 5.10](#) (the minimum dose is 240 mg/m²).

Additional details of the study design and escalation decisions are in [Section 9](#).

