8.2 Sample Size Determination

The study will enroll up to 24 patients in the dose escalation phase. Once the MTD is established, accrual may continue in the dose expansion phase with the objective of studying 6 additional patients at the MTD dose determined in the escalation phase.

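### Section 8.6 says expansion monitoring will keep the DLT risk at or below 30%, a property that neither of the protocol's six-patient triggers has

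*Protocol*

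**What the plan says.** Section 8.6 gives the purpose of monitoring in the expansion phase: "Expansion patients will continue to be monitored for safety to ensure that the DLT risk does not exceed 30" percent. The cohort is capped: "A maximum of 6 patients will be enrolled in the expansion cohort, dosed at the MTD". The next sentence turns the purpose into a rule: "if more than 2 patients in the expansion cohort experience a DLT, an ad hoc SRC meeting may be convened". Section 8.6 gives no firing probabilities for this rule and does not say how escalation patients at the same dose enter the judgement.

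Section 4.1.2 has a different trigger for the same cohort: "If 2 of the first 5 patients or if ≥ 2 of 6 patients experience a DLT", the Principal Investigator discusses with the investigators and the Medical Monitor and/or SRC whether more patients are needed to reassess the MTD. It adds: "Monitoring of all safety and toxicity data will be done by the Principal Investigator and the SRC on a real-time basis".

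Section 8.4.8 sets the target DLT risk at 30% with a target range of 23.6% to 35.9%. Doses are dropped when the probability that the DLT rate exceeds 30% reaches 95%. Section 8.4.6 summarises the proportion of patients with a DLT by dose level and makes exact 95% intervals optional.

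**The concern.** Section 8.6 attaches a numerical ceiling to the monitoring and names the rule meant to deliver it. A rule on six patients can pick up a grossly toxic dose, but it cannot hold the risk under 30% or show that it is under 30%.

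This matters because the protocol's own simulations show that escalation can pass an over-toxic dose to expansion. In Table 11, Scenario 5 selects the dose with a 40% DLT rate in 61.2% of trials, Scenario 1 selects the 47% dose in 24.6%, and Scenario 2 selects the 45% dose in 19.6%. If the SRC or a later Phase 2 team takes the sentence at face value, they could give a quiet expansion cohort more weight than it can bear.

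**Working it through.** **Inputs.** Cohort of 6 (Sections 8.2 and 8.6); trigger of 3 or more DLTs (8.6); trigger of 2 or more (4.1.2); target 30% and range 23.6% to 35.9% (8.4.8). The true risks of 40%, 45% and 50% are chosen for illustration; 40% and 45% also occur in Table 11.

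**1. Reproducing the plan's own figures.** Take φ = 0.30 and the usual BOIN defaults p1 = 0.6φ = 0.18 and p2 = 1.4φ = 0.42. The protocol does not state these defaults, so they are an assumption.

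- Lower limit: ln(0.82/0.70) / ln[(0.30×0.82)/(0.18×0.70)] = 0.2365
- Upper limit: ln(0.70/0.58) / ln[(0.42×0.70)/(0.30×0.58)] = 0.3585

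Both match the stated range. The elimination rows of Table 10 also follow from a uniform prior (again assumed). The posterior probability of a rate above 30% is 0.992 for 3/3, 0.971 for 4/6, 0.953 for 5/9 and 0.982 for 7/12. With one DLT fewer it is 0.916, 0.874, 0.850 and 0.938, all below 0.95.

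**2. Firing probabilities.** X is Binomial(6, p). The Section 8.6 rule is silent when X ≤ 2, with probability (1−p)^6 + 6p(1−p)^5 + 15p²(1−p)^4. At p = 0.40 this is 0.0467 + 0.1866 + 0.3110 = 0.544. In a completed cohort of six, 2 DLTs among the first five already imply at least 2 of six, so the Section 4.1.2 rule is silent when X ≤ 1. At p = 0.40 this is 0.0467 + 0.1866 = 0.233.

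| True DLT risk | 8.6 (≥3 of 6): fires | silent | 4.1.2 (≥2 of 6): fires | silent |
|---|---|---|---|---|
| 30% | 25.6% | 74.4% | 58.0% | 42.0% |
| 40% | 45.6% | 54.4% | 76.7% | 23.3% |
| 45% | 55.9% | 44.2% | 83.6% | 16.4% |
| 50% | 65.6% | 34.4% | 89.1% | 10.9% |

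At 35.9%, the upper end of the target range, the Section 8.6 rule is silent in 62.9% of cohorts. Its silence falls below 20% only near a true risk of 60% (17.9%).

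**3. What a silent cohort shows.** The one-sided 95% Clopper-Pearson upper bound for 0 of 6 is 1 − 0.05^(1/6) = 39.3%. For 1 of 6 it is 58.2% and for 2 of 6 it is 72.9%. A result of 0 of 6 sets off neither trigger and still does not exclude 30%. At a true risk of exactly 30%, 0 of 6 occurs with probability 0.7^6 = 11.8%.

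**4. Pooling with escalation patients.** Up to 12 escalation patients may already have been treated at the dose. With 18 in total, the one-sided 95% upper bound is 23.8% for 1 DLT, 31.0% for 2 and 37.7% for 3. Pooling narrows the uncertainty, but a bound below 30% needs 0 or 1 DLT in 18. At a true rate of 30% that has probability 0.7^18 + 18×0.3×0.7^17 = 0.0016 + 0.0126, about 1.4%.

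**The case against.** The best defence is that Section 8.6 does not stand alone. Section 4.1.2 has the lower trigger count and says that discussion will follow, and it requires real-time review. Section 5.10 provides for halts on repeated SAEs or unacceptable toxicity, and Section 7.1.3.2 sets the RP2D after review of the safety data at each dose level. Section 8.4.6 already reports the DLT proportion by dose level, with separate escalation and expansion summaries only as an optional extra. Section 8.1 says that all analyses are descriptive. On this view, the verb in Section 8.6 states an aim and is not a decision criterion.

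Much of this stands, and it rules out three stronger readings.

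- A reader might infer that the protocol's only check on the expansion dose is the Section 8.6 trigger, so that a 40% risk escapes more often than not. The 54.4% belongs to the Section 8.6 rule alone; under Section 4.1.2 the figure is 23.3%.
- A reader might infer that a quiet cohort will be reported as proof of a risk of at most 30%. No section says so.
- A reader might infer that the upper bound ought to be required to fall below 30%. The design seeks a dose near 30%, and a dose with a true rate of exactly 30% would pass that test only about 1.4% of the time.

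The defence does not rescue the sentence itself. It names a ceiling and then specifies the rule that is to hold it. Neither trigger has that property, both lead only to discussion, and the real-time review has no numerical criterion. Nor is this a matter left to the SAP, because the protocol itself fixes both the claim and the rule.

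**Conclusion.** The point holds as a minor one. Section 8.6 states a safety property that its trigger lacks, and Section 4.1.2's trigger lacks it too. Changing the count does not help. At 3 or more of 6 the rule misses a 40% risk in 54.4% of cohorts; at 2 or more it still misses 23.3% and fires in 58.0% of cohorts at a risk of exactly 30%. The sentence also sits badly with Section 8.4.8: a dose properly selected under a target range reaching 35.9% may have a true risk above 30%.

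The figures assume six DLT-evaluable expansion patients with independent outcomes and a common risk. With fewer patients, both triggers would be silent more often. The 39.3% bound describes the expansion cohort alone and takes no account of escalation data at the dose. The defect lies in wording and justification and does not touch the escalation design or dose assignments.

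**What to change.** In Section 8.6:

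- Replace the stated purpose with wording such as: to detect a markedly excessive DLT rate.
- Reconcile the trigger with Section 4.1.2, so that the protocol contains one rule for this cohort, and print that rule's firing probabilities at true DLT risks of 30%, 40% and 50%. Which rule to keep is for the sponsor and the SRC.
- State that the acceptability of the MTD/RP2D will be judged on the DLT rate of all DLT-evaluable patients treated at that dose, escalation and expansion together. Report it with an exact interval, or with the posterior probability that the rate exceeds 30%, which Section 8.4.8 already uses.
- Do not add a requirement that the upper bound lie below 30%.

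The cost is a few lines of text and one line in the DLT table, with no extra patients or procedures. The downside is that the protocol then offers a weaker assurance than it does now.

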9 SUPPORTING DOCUMENTATION AND OPERATIONAL CONSIDERATIONS

9.1 Appendix 1: Regulatory, Ethical, and Study Oversight Considerations

9.1.1 *Regulatory and Ethical Considerations*

- This study will be conducted in accordance with the protocol and with the following:
 - Consensus ethical principles derived from international guidelines including the Declaration of Helsinki and Council for International Organizations of Medical Sciences (CIOMS) International Ethical Guidelines
 - Applicable International Council for Harmonisation (ICH) and Good Clinical Practice (GCP) Guidelines
 - Applicable laws and regulations
- The protocol, protocol amendments, ICF, Investigator Brochure, and other relevant documents (eg, advertisements) must be submitted to an IRB/IEC by the Investigator and reviewed and approved by the IRB/IEC before the study is initiated.
- Any amendments to the protocol will require IRB/IEC approval before implementation of changes made to the study design, except for changes necessary to eliminate an immediate hazard to study patients.
- The Investigator will be responsible for the following:
 - Providing written summaries of the status of the study to the IRB/IEC annually or more frequently in accordance with the requirements, policies, and procedures established by the IRB/IEC
 - Notifying the IRB/IEC of SAEs or other significant safety findings as required by IRB/IEC procedures
 - Providing oversight of the conduct of the study at the site and adherence to requirements of the Code of Federal Regulations (21 CFR), ICH guidelines, the IRB/IEC, European regulation 536/2014 for clinical studies (if applicable), and all other applicable local regulations

9.1.2 *Financial Disclosure*

Investigators and Subinvestigators will provide the Sponsor with sufficient, accurate financial information as requested to allow the Sponsor to submit complete and accurate financial certification or disclosure statements to the appropriate regulatory authorities. Investigators are responsible for providing information on financial interests during the course of the study and for 1 year after completion of the study.

9.1.3 Informed Consent Process

- The Investigator or their representative will explain the nature of the study to the patient or their legally authorized representative and answer all questions regarding the study.
- Patients must be informed that their participation is voluntary. Patients or their legally authorized representatives will be required to sign a statement of informed consent that meets the requirements of 21 CFR 50, local regulations, ICH guidelines, Health Insurance Portability and Accountability Act (HIPAA) requirements, where applicable, and the IRB/IEC or study center.
- The medical record must include a statement that written informed consent was obtained before the patient was enrolled in the study and the date the written consent was obtained. The authorized person obtaining the informed consent must also sign the ICF.
- Patients must be re-consented to the most current version of the ICF(s) during their participation in the study.
- A copy of the ICF(s) must be provided to the patient or the patient's legally authorized representative.

A patient who is rescreened is required to sign another ICF.

9.1.4 Data Protection

- Patients will be assigned a unique identifier by the Sponsor. Any patient records or datasets that are transferred to the Sponsor will contain the identifier only; patient names or any information which would make the patient identifiable will not be transferred.
- The patient must be informed that their personal study-related data will be used by the Sponsor in accordance with local data protection law. The level of disclosure must also be explained to the patient.
- The patient must be informed that their medical records may be examined by Clinical Quality Assurance auditors or other authorized personnel appointed by the Sponsor, by appropriate IRB/IEC members, and by inspectors from regulatory authorities.

9.1.5 Safety Review Committee

The study will be overseen by an SRC composed of 3 voting members (the Medical Monitor and two additional members). The SRC will convene to review data and discuss next steps at the end of every dose level (once all patients complete the 10-week evaluation period), when the data have been cleaned, and the DLT outcomes are determined. In addition, the SRC will meet every 6 months at minimum, and as needed to review AEs. The Principal Investigator and study biostatistician will attend SRC

meetings. The SRC will sign off on each dose level before activation of a new dose cohort or expansion of a dose cohort may begin.

9.1.6 *Dissemination of Clinical Study Data*

This study will be posted on clinicaltrials.gov. Publication policies are described in [Section 9.1.11](#).

9.1.7 *Data Quality Assurance*

- All patient data relating to the study will be recorded on printed or electronic CRF (eCRF) unless transmitted to the Sponsor or designee electronically (eg, laboratory data). The Investigator is responsible for verifying that data entries are accurate and correct by physically or electronically signing the CRF.
- The Investigator must maintain accurate documentation (source data) that supports the information entered in the CRF.
- The Investigator must permit study-related monitoring, audits, IRB/IEC review, and regulatory agency inspections and provide direct access to source data documents.
- Monitoring details describing strategy (eg, risk-based initiatives in operations and quality such as Risk Management and Mitigation Strategies and Analytical Risk-Based Monitoring), methods, responsibilities and requirements, including handling of noncompliance issues and monitoring techniques (central, remote, or on-site monitoring) are provided in the Monitoring Plan.
- The Sponsor or designee is responsible for the data management of this study including quality checking of the data.
- The Sponsor assumes accountability for actions delegated to other individuals (eg, contract research organizations).
- Study monitors will perform ongoing source data verification to confirm that data entered into the CRF by authorized site personnel are accurate, complete, and verifiable from source documents; that the safety and rights of patients are being protected; and that the study is being conducted in accordance with the currently approved protocol and any other study agreements, ICH GCP, and all applicable regulatory requirements.

9.1.8 *Source Documents*

- Source documents provide evidence for the existence of the patient and substantiate the integrity of the data collected. Source documents are filed at the Investigator's site.
- Data reported on the CRF or entered in the eCRF that are transcribed from source documents must be consistent with the source documents or the discrepancies must be explained. The Investigator may need to request previous medical records

or transfer records, depending on the study. Also, current medical records must be available.

- The definition of what constitutes source data can be found in the Monitoring Plan.

9.1.9 Quality Assurance

Adherence to Protocol Therapy: Screening/baseline source documentation will be submitted stored locally and securely in the study database. As a quality assurance measure for the treatment delivered on this protocol, primary patient records may be reviewed. The records to be examined will be selected retrospectively and at random; complete records must therefore be maintained on each patient treated on the protocol. These records should include primary documentation (eg, laboratory report slips, imaging reports, pathology reports, physician notes, etc), which confirm that:

- The patient met each eligibility criterion.
- Signed informed consent was obtained prior to treatment.
- Treatment was given according to protocol (dated notes about doses given; any reasons for any dose modifications).
- Toxicity was assessed according to protocol (laboratory report slips, etc).
- Response was assessed according to protocol (MRI scan, lab reports, dated notes on measurements and clinical assessment, as appropriate).

9.1.10 Study and Site Closure

The Sponsor reserves the right to close the study site or terminate the study at any time for any reason at the sole discretion of the Sponsor. Study sites will be closed upon study completion. A study site is considered closed when all required documents and study supplies have been collected and a study-site closure visit has been performed.

The Investigator may initiate study-site closure at any time, provided there is reasonable cause and sufficient notice is given in advance of the intended termination.

Reasons for the early closure of a study site by the Sponsor or Investigator may include but are not limited to:

- Failure of the Investigator to comply with the protocol, the requirements of the IRB/IEC or local health authorities, the Sponsor's procedures, or GCP guidelines
- Inadequate recruitment of patients by the Investigator
- Discontinuation of further study intervention development

9.1.11 Publication Policy

- The results of this study may be published or presented at scientific meetings. If this is foreseen, the Investigator agrees to submit all manuscripts or abstracts to

the Sponsor before submission. This allows the Sponsor to protect proprietary information and to provide comments.

- The Sponsor will comply with the requirements for publication of study results. In accordance with standard editorial and ethical practice, the Sponsor will generally support publication of multicenter studies only in their entirety and not as individual site data. In this case, a coordinating Investigator will be designated by mutual agreement.
- Authorship will be determined by mutual agreement and in line with International Committee of Medical Journal Editors (ICMJE) authorship requirements.

9.2 Appendix 2: Radiotherapy Treatment Considerations and Planning

9.2.1 Treatment Volumes

The goal of the treatment planning process is to deliver a uniform dose to a planning target volume (PTV) which includes all known tumor plus a specified margin. The volume of normal brain outside the PTV receiving > 95% of the prescription dose should be minimized. For treatment planning, the targets are defined below.

9.2.1.1 Gross Tumor Volumes (GTV)

GTV1 (for initial phase of RT): The GTV1 is the T1 enhancing and nonenhancing tumor volume (T2 or FLAIR) as visualized on the baseline MRI scan. In cases when another MRI is performed for protocol eligibility, for RT planning, or for clinical reasons, the target identified on the more recent MRI should be used for treatment planning.

GTV2 (for conedown phase of RT): The GTV2 is the T1 enhancing tumor volume as visualized on the postoperative Day 0/1 MI scan. This would include the resection cavity in patients undergoing resection. In cases when another MRI is performed for protocol eligibility, for radiation treatment planning, or for clinical reasons, the target identified on the more recent MRI should be used for treatment planning.

9.2.1.2 Clinical Target Volume (CTV)

The CTV is the GTV plus a margin of 5 mm in all directions. However, the CTV must not extend outside the brain and should be limited by the edge of brain as areas outside the brain are rarely affected by tumor. Care must be taken when extending it inferiorly to minimize the amount of normal cervical spinal cord included. Margin may be reduced at true anatomic boundaries (eg, bone, nonviolated tentorium, ventricle, etc). In uncommon cases where an MRI cannot be utilized for treatment planning due to a pacemaker or other factor, an additional 1-cm margin rather than 5-mm margin should be added to define the CTV1 and CTV2 to the MRI-based definitions below.

CTV1: The CTV1 is the GTV1 plus a margin of 5 mm in all directions, with consideration of the factors described above.

CTV2: The CTV2 is the GTV2 plus a margin of 5 mm in all directions, with consideration of the factors described above.

9.2.1.3 *Planning Target Volumes (PTV)*

The PTV is the CTV plus a margin in all directions to account for daily setup variation and patient movement, but not beam penumbra or build-up. The margin should not exceed 5 mm and will commonly be 3-5 mm depending upon immobilization device and frequency of image guidance. Individual institutions are encouraged to perform studies defining the appropriate PTV margin based upon institutional immobilization and localization procedures.

As the PTV is not structure limited, it may extend into and below the skull. There is no need to adjust dosimetry of the treatment plan to ensure full target dose to the skin and bone itself as the tumor will not be present there, regardless of positioning uncertainty included with the PTV margins (ie, there is no need to use bolus to increase dose outside the intracranial space).

PTV1: The PTV1 is the CTV1 plus a margin all directions to account for daily setup variation and patient movement (typically 3-5 mm). Adjust for skin avoidance as described above.

PTV2: PTV2 is the CTV2 plus a margin all directions to account for daily setup variation and patient movement (typically 3-5 mm). Adjust for skin avoidance as described above.

9.2.2 *Target Dose*

The total dose to the prescription point will be 6000 cGy in 30 daily fractions of 200 cGy each. PTV1 will receive 4600 cGy in 23 fractions. PTV2 will receive an additional 1400 cGy in 7 fractions (total 6000 cGy in 30 fractions).

9.2.3 *Prescription Point*

For 3D treatment planning, the prescription point is at or near the isocenter. The goal of the treatment plan is to encompass at least 97% of the PTV within the 95% isodose surface. IMRT plans may be prescribed to an isodose line provided that dose uniformity guidelines are met. It is recognized that these goals may not be achieved at the discretion of the treatment team if necessary to protect critical tissues.

9.2.4 *Dose Definition*

The absorbed dose is specified as cGy to muscle.

9.2.5 *Tissue Heterogeneity*

Calculations shall take into account the effect of tissue heterogeneities.

9.2.6 *Dose Uniformity*

For conformal planning techniques (3D CRT and IMRT), the 99% PTV shall be encompassed within the 95% isodose surface and no more than 10% of the PTV should receive more than 105% of the prescription dose, as evaluated by dose volume histogram.

